4.1 Primary Outcome Measures

4.1.1 Primary Efficacy Outcome Measure

Measure Title: *Percentage of Participants with Sustained Virologic Response 12 (SVR12)*

Measure Description: *SVR12 was defined as plasma HCV RNA less than the lower limit of quantification (LLOQ) from the earliest sample drawn at least 22 weeks following study treatment initiation (i.e. at a visit scheduled at least 10 weeks after scheduled end of study treatment). Participants without any HCV RNA result at least 22 weeks after treatment initiation will be considered as having HCV RNA greater than the LLOQ.*

A two-sided 95%, confidence interval was calculated for this percentage using the Wilson (score) method.

Time Frame: *At least 22 weeks and up to 76 weeks from treatment initiation.*

Population Description: *Participants who enrolled and received first dose of study medication.*

Associated study objective: *“To estimate SVR (defined as HCV RNA < lower limit of quantification [LLOQ] at least 10 weeks after the end of treatment [EOT] [which is at least 22 weeks from the study entry visit date]).”*

Details: Due to the definition of SVR outcome measure, missing HCV RNA results will lower the overall percentage of participants with SVR. Therefore, various reasons for non-SVR (e.g., discontinued treatment early due to various reasons including intolerance, observed HCV RNA \geq LLOQ, missing evaluation for SVR (and reasons as known), and the number of participants meeting each reason for non-SVR, will be presented in order to interpret the overall SVR sample estimate.

For interim analyses: Interim analysis is planned when SVR outcomes are available for approximately 100 participants. At interim reviews, SVR will be calculated only among those with potential to contribute to SVR (by having at least 22 weeks elapsed since study entry). Imputation of missing SVR evaluation as non-SVR response will only occur for participants for whom more than 76 weeks since study enrollment has elapsed. In other words, early study discontinuations prior to week 22 will not be counted in SVR estimation at interim review, as these could bias the estimation of SVR towards futility. Instead, these early study discontinuations prior to week 22 (before available for SVR evaluation), and others missing SVR evaluation, will contribute to the interim monitoring

trigger. For more details, refer to Overview of Formal Interim Monitoring of section 3.5 above.

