5.1.2 Administration and Duration

Participants will take SOF/VEL orally once daily with or without food and will receive treatment for a duration of 12 weeks. Study staff will observe the first dose being taken by the participant upon completion of all entry evaluations. Participants should be instructed to open and finish one bottle of study product at a time. When the participant takes the last pill of SOF/VEL from each bottle, he/she will be instructed to contact the site to report the completion of the bottle. Participants will, therefore, contact a site a maximum of three times to indicate completion of a bottle. See A5360 MOPS for additional information on reporting of treatment stop date.

In the scenario of lost study medication, the participant will be asked to contact the study site as soon as possible. If the participant has been off study medication less than 2 weeks (≤ 14 days), he/she will be eligible for a one-time replacement of study medication to complete the 12 week course. Participants who report a subsequent loss of study medication will not be eligible for replacement and will enter the follow-up phase (week 24 visit). If the participant has not taken study medication for more than 2 weeks (≥ 15 days), study medication will not be replaced and the participant will enter the follow-up phase (week 24 visit).

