6.2.4 Post-Entry Evaluations

Given the design of the MINMON strategy, there will be no on-treatment or EOT evaluations. See section 6.3.22 for post-entry site contact with participants via remote mechanism.

Post-Treatment Evaluations

Step 1: Following treatment completion at week 12, participants will undergo evaluations as outlined in the SOE 6.1-1.

NOTE: If the participant comes in for the week 24 visit during the -14 days window (i.e., week 22), then the week 22 remote call is not needed.

Week 24/SVR Evaluation Visit

The week 24 visit (visit window: week 22-28) is ideally the visit where SVR should be assessed for all participants, and subsequently they will be registered to Step 2. However, if a participant misses the visit window (>week 28), the week 24 visit will be considered a missed visit and he/she will need to be scheduled for an SVR visit prior to being registered to Step 2 of the study. The SVR visit can

take place at any time point after week 28 and up to week 72 and is mandatory for the participant to be registered to Step 2.

NOTE: Participants will be reminded of the week 24/SVR visit during the remote contact (at weeks 4 and 22), and participants only need to complete either the week 24 OR the SVR evaluation visit; they will not be required to complete both. If a participant completes week 24, his/her next visit will be at week 48 on Step 2. If a participant misses the week 24 visit and returns to the clinic for the SVR visit either at week 48 or 72, then only the SVR evaluations will be performed at that visit time point. Evaluations for weeks 48 or 72 will be performed at the next scheduled study visit. However, if a participant completes their SVR visit at week 72, this visit will be the participants' last study visit and they will not enter Step 2.

Step 2 Registration

Following completion of the SVR evaluation on Step 1 (Week 24 OR SVR visit), participants will be registered to Step 2 on that same day. Participants will undergo evaluations as outlined in the SOE 6.1-2, within the ±28-days visit window, as appropriate for the visit.

NOTE: Participants who register into Step 2 within the week 48 visit window will complete the week 48 and 72 visits. If a participant registers into Step 2 after the week 48 visit window, site staff should have the participant return to the clinic to complete week 72 (final study visit).

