6.3.10 Clinical Assessments

Complete Physical Exam

A complete physical examination must be performed at screening and is to include at a minimum an examination of the skin, head, mouth, and neck; auscultation of the chest; cardiac exam; abdominal exam; and examination of the lower extremities for edema. The complete physical exam will also include signs and symptoms, diagnoses, and vital signs (height, weight, temperature, pulse, respiration rate, and blood pressure).

Targeted Physical Exam

A targeted physical examination should be performed at entry, week 24/SVR evaluation visit and weeks 48 and 72, and should include vital signs (weight, temperature, pulse, respiration rate, and blood pressure), and is to be driven by any previously identified or new AE/targeted condition (as described in below bullets), that the participant has experienced within 14 days prior to study entry/since the last visit or at this visit.

Post entry, record the following targeted events regardless of grade:

- Uterine pregnancy
- AIDS-defining conditions (refer to the CDC HIV Classification and the WHO Staging System for HIV Infection and Disease)
- Tuberculosis
- Chronic HBV
- Ascites
- Hepatic Encephalopathy

Refer to section 7.2 for AE collection requirements.

Height

Height (in cm) will be collected once at study screening.

Weight

Weight (in kg) will be collected at study screening, entry, week 24/SVR evaluation visit, and weeks 48 and 72.

Concomitant Medications

At entry and at the week 24/SVR evaluation visit, new and discontinued concomitant medications should be recorded on the eCRFs. See section 5.4 for concomitant medications.

Study Treatment (Intervention) Modifications

When the participant takes the last tablet of each bottle of SOF/VEL, they will be instructed to contact the site to report the treatment stop date. This information self-reported by the participant should be captured on the eCRF when reported outside of and during the week 24/SVR evaluation visit. See A5360 MOPS for additional details.

At the week 24/SVR evaluation visit, record all study drug modifications, including participant-initiated modifications, inadvertent and deliberate interruptions of more than 7 days. Record permanent discontinuation of study treatment (see section 6.2.7).

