10.2 Outcome Measures

10.2.1 Primary Outcome Measures

- 10.2.1.1 Efficacy: Sustained virologic response defined as <LLOQ of HCV RNA in plasma from the earliest sample drawn at least 22 weeks following study entry. Missing results will be treated as SVR non-responders.
- 10.2.1.2 Safety: SAEs as defined by International Council for Harmonization (ICH) guidelines occurring from study entry until 24 weeks following study entry.

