5.1 General Considerations

5.1.1 Definitions

Baseline: Any characteristic measured or evaluated prior to the first dose of study medication (including information collected at screening) can be used as a ‘baseline’ characteristic. Areas where use of screening could induce bias (due to eligibility criteria) will be noted in any analysis, as applicable.

SVR: Target not detected (TND) result is a valid that also qualifies as <LLOQ and will be counted as an SVR responder. When handling of multiple HCV RNA results, the valid result from the earliest sample drawn within the SVR evaluation window (starting 22 weeks post study treatment initiation) will be used for analysis.

Reference Start Dates:

- Study enrollment date: Date participant was enrolled on study.
- Treatment start date: Date participant took first dose of study treatment.

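### The SVR rule sets no condition on non-study HCV treatment, so a participant first sampled during or after outside treatment counts as a MINMON responder

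*SAP*

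**What the plan says.** Protocol 10.2.1 gives the primary efficacy outcome as "Sustained virologic response defined as <LLOQ of HCV RNA in plasma from the earliest sample drawn at least 22 weeks following study entry", with missing results scored as non-response. SAP 4.1.1 repeats the rule counted from treatment initiation ("SVR12 was defined as plasma HCV RNA less than the lower limit of quantification (LLOQ) from the earliest sample drawn at least 22 weeks following" that date), with the time frame "At least 22 weeks and up to 76 weeks from treatment initiation". SAP 5.1.1 settles multiple results by taking "the valid result from the earliest sample drawn within the SVR evaluation window". The analysis set is everyone who took a first dose (SAP 5.1.3).

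The objective behind the outcome (protocol 1.2.1, repeated in SAP 3.3.1) is HCV RNA below the LLOQ at least 10 weeks after the end of treatment, which it equates with at least 22 weeks from entry.

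Other sections shape who reaches the SVR sample, and when:

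- Protocol 5.1.2 on repeated drug loss: "Participants who report a subsequent loss of study medication will not be eligible for replacement and will enter the follow-up phase (week 24 visit"). Participants off drug for 15 days or more also get no replacement.
- Protocol 9.1 lists further reasons for stopping early, including toxicity, prohibited medication, pregnancy and participant request. Section 6.2.7 leaves the SVR timing unchanged for early stoppers.
- Protocol 6.2.4: if the week 24 visit is missed, the SVR visit can "take place at any time point after week 28 and up to week 72".
- Protocol 6.3.10: "At entry and at the week 24/SVR evaluation visit, new and discontinued concomitant medications should be recorded on the eCRFs".

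Neither document has a non-responder rule, a stated treatment-policy intention or a sensitivity analysis for HCV treatment obtained outside the study. The reasons for non-SVR in protocol 10.6.1 and SAP 4.1.1 are descriptive. They reclassify nobody whose RNA is below the LLOQ.

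**The concern.** The scoring rule is complete as written: one sample, one threshold, everyone dosed. Applied literally, it credits the MINMON course with a viral result that another course may have produced. It can even accept a sample taken while the outside course is still running.

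This would fall on people for whom the strategy did not go to plan: those who lost drug, stopped early or missed week 24. The trial has one arm, so no comparator would absorb the error. The estimate is read against two benchmarks. HIGH suggests that a randomised trial may not be needed, and LOW suggests that the approach should be reconsidered. A false responder would also enter the responder-only sets for reinfection and FIB-4 change, and would count as an SVR attained in the cost analysis.

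**Working it through.** **1. Who is affected.** Take each possible sequence under the earliest-sample rule.

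| Sequence | Scored as | Affected? |
|---|---|---|
| First sample at weeks 22–28 quantifiable, outside treatment later | Non-responder, fixed by the first sample | No |
| First sample at weeks 22–28 below LLOQ, no outside treatment before it | Responder | No |
| Stops or loses drug, treated elsewhere, first sample at weeks 22–28 below LLOQ | Responder | Yes |
| Misses week 24, treated elsewhere, first sample after week 28 below LLOQ | Responder | Yes |
| No sample by week 76 | Non-responder | No |

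**2. Where the rule and the objective part.** The 22-week criterion stands in for 10 weeks after treatment because 12 + 10 = 22. That equivalence needs treatment to end by week 12. Illustration (assumed dates): a participant stops at week 4, starts an outside 12-week course at week 8, finishes at week 20 and is sampled at week 22. The sample is 22 − 20 = 2 weeks after the last HCV treatment, yet it meets the scoring rule. On the late route, the first sample can fall 72 − 12 = 60 weeks after planned end of treatment, or 64 weeks at the week 76 limit.

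**3. The plan's own cut-offs.** Wilson 95% limits for x/n, with p = x/n, n = 400 and z = 1.96:

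(p + z²/2n ± z√[p(1−p)/n + z²/4n²]) / (1 + z²/n)

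| Responders | Rate | Lower | Upper | Benchmark |
|---|---|---|---|---|
| 371 | 92.75% | 89.78% | 94.90% | LOW met |
| 372 | 93.00% | 90.07% | 95.11% | neither |
| 391 | 97.75% | 95.78% | 98.81% | neither |
| 392 | 98.00% | 96.10% | 98.98% | HIGH met |

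These reproduce the cut-offs in protocol Table 10.4-1 (at least 392; at most 371). The exact binomial probabilities also agree: P(HIGH) is .15 at a true 97% and .59 at 98%; P(LOW) is .45 at 93% and .17 at 94%.

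**4. Size per person.** 1/400 = 0.25 points. The documents give no rate of outside treatment, so the number moved, k, is an assumption, shown here from 1 to 8 (0.25 to 2 points):

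- 392 observed, k = 1: 391, HIGH lost.
- 372 observed, k = 1: 371, LOW newly met.
- 376 observed, k = 4: 372, neither; k = 6: 370 (89.50–94.70%), LOW met.
- 380 observed, k = 8: 372, neither, so no change.

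**5. How often one person decides.** The probability of exactly 372 or 392 responders at n = 400 is 7.8% at a true rate of 93%, 1.8% at 95%, 1.3% at 96%, 6.5% at 97% and 14% at 98%.

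**6. If it were larger.** Suppose outside treatment added a full point (4 of 400). At a true 97%, P(HIGH) would rise from .15 to .59. At a true 93%, P(LOW) would fall from .45 to .17. This shows sensitivity only; nothing in the documents says that four such cases are likely.

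**The case against.** The strongest reply is that this is a rare event.

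- Protocol 6.2.4 has no on-treatment or end-of-treatment evaluations, and 6.2.6 discourages HCV RNA testing at unplanned visits. Few participants would therefore know before the SVR sample that treatment had failed.
- The week 22 contact and the attendance incentive are there to limit late first samples.
- Access to outside treatment varies. Section 2.1 reports approval of generic SOF/VEL in India, but also says that price kept sofosbuvir and daclatasvir out of reach in Thailand.
- Some early stoppers may have been cured by the study drug they took, so not everyone treated elsewhere is a false responder.
- The separate analysis implementation plan, which is not among these documents, may hold a coding rule.

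The first four points stand and keep the expected number low. The last reduces certainty, but an implementation document should not have to override the outcome definition in the SAP.

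A treatment-policy definition can be legitimate if declared. Here it is not declared, and in a single-arm estimate of SVR from the MINMON course it would not answer objective 1.2.1.

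Three stronger readings are tempting, and the documents do not support them:

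- **Every result below the LLOQ up to week 76 counts as success, so week 24 failures who are re-treated become responders.** The earliest valid sample decides, and a quantifiable first result is final.
- **SVR is biased upward overall.** The same definition scores every missing result as failure, including true cures, which pushes the other way. The net direction is not established.
- **A shift of about a point would cover the whole distance between benchmarks.** The 95% and 96% values apply to confidence limits. The observed cut-offs are 392 − 371 = 21 participants apart, or 21/400 = 5.25 points.

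**Conclusion.** The point holds in a limited form. The SVR definition has no condition on non-study HCV treatment, so it gives a wrong result for one group: participants whose first qualifying sample is drawn during or after outside treatment and is below the LLOQ. For them the scoring departs from the plan's own objective, and no other section corrects it.

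The error from this mechanism is one-directional, at 0.25 points per person. The number of people is not given in the documents and is probably small. One case matters to a benchmark only at exactly 372 or 392 responders; in mid-range, at 380 for example, even eight change nothing. The case for acting is that the rule costs little to state now. Deciding individual cases after the results are known could settle a benchmark post hoc.

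**What to change.** Add to protocol 10.2.1 and SAP 4.1.1, with a cross-reference in SAP 5.1.1: a participant with recorded non-study anti-HCV treatment started between entry and the SVR sample is an SVR non-responder in the primary analysis. State that study-supplied replacement drug under protocol 5.1.2 is not non-study treatment.

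- Identify cases from the concomitant-medication eCRF at the week 24/SVR visit. Participants without that visit and without a result are already non-responders.
- Report the number as its own category among the reasons for non-SVR.
- Add a sensitivity analysis scoring these participants on observed HCV RNA, since study drug may have cured some of them.

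The cost is a sentence in each document, one table row and one extra Wilson interval, using data the protocol already collects. The primary SVR estimate may be slightly lower, and a participant cured by study drug before taking other treatment would be scored as a failure; the sensitivity analysis shows how much that matters. The change concerns outcome scoring only, not clinical management.

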4.1.2 Primary Safety Outcome Measure

Measure Title: Percentage of Participants with an Occurrence of Serious AEs According to ICH Criteria

Measure Description: Serious adverse events (SAEs) as defined by International Council for Harmonization (ICH) guidelines occurring from treatment initiation until 28 weeks following treatment initiation (end of week 24 visit window)

A two-sided, 95% confidence interval was calculated for the percentage using the Wilson (score) method.

Time Frame: Within 28 weeks following treatment initiation.

Population Description: Participants who received first dose of study medication and had at least one post-entry evaluation for adverse events.

Associated study objective: “To summarize the occurrence of serious adverse events (SAEs) within 24 weeks following study entry.”

Details: All SAEs meeting this outcome measure will be summarized and described. Note, the timing above applies to the timing of the event occurrence, and not to when the event was reported. For example, an event occurring at week 23 might not be reported until the week 48 clinic visit. Also, a clinic visit is not required for “evaluation for adverse events”; the reporting of an AE qualifies as meeting this criterion. This allows exclusion of participants who are lost after initial dose with no information on AEs following initiation of study treatment.

4.2 Secondary Outcome Measures

4.2.1 Secondary Outcome Measure #1 – Unplanned clinic visits

Measure Title: *Percentage of Participants with at Least One Unplanned Clinic Visit Prior to SVR12 Evaluation*

Measure Description: *According to the study minimal monitoring intervention, there were no planned clinic visits prior to study week 24, when SVR12 was scheduled to be evaluated.*

A two-sided, 95% confidence interval was calculated for the percentage using the Wilson (score) method.

Time Frame: *From treatment initiation to week 22.*

Population Description: *Participants who enrolled and received first dose of study medication.*

Associated study objective: *“To estimate the proportion of participants with unplanned clinic visits prior to SVR evaluation.”*

Details: *Number, reasons for and timing of unplanned clinic visits will also be summarized.*

4.2.2 Secondary Outcome Measure #2 – Other AEs

Measure Title: *Percentage of Participants with an occurrence of one or more non-serious, Grade >= 3 Adverse Event, or treatment limiting AE.*

Measure Description: *AEs included all primary diagnoses, primary signs/symptoms, and primary laboratory abnormalities that either had severity grade ≥ 3 or led to a change in study medication. SAEs by ICH criteria were excluded as they contributed to the primary safety outcome measure.*

A two-sided, 95% confidence interval was calculated for the percentage using the Wilson (score) method.

Time Frame: *Within 28 weeks following treatment initiation.*

Population Description: *Participants who received first dose of study medication and had at least one post-entry evaluation for adverse events.*

Associated study objective: *“To summarize the occurrence of adverse events, other than SAEs, within 24 weeks following study entry.”*

Details: All AEs meeting this outcome measure will be enumerated, and summarized by MeDdRA categorization (SOC and HLT).

Division of AIDS Table for Grading the Severity of Adult and Pediatric Adverse Events (DAIDS AE Grading Table), corrected Version 2.1, July 2017, used for severity grading.

Note, the timing above applies to the timing of the event and not to when the event was reported. For example, an event occurring at week 23 might not be reported until a week 48 clinic visit. Also, a clinic visit is not required for “evaluation for adverse events”; the reporting of an AE qualifies as meeting this criterion. This allows exclusion of participants who are lost after initial dose with no information on AEs following initiation of study treatment.

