7.2 Adverse Event Collection Requirements for This Protocol

Post-entry, all AEs must be recorded on the eCRFs if any of the following criteria have been met.

- All grade ≥ 3 AEs
- All AEs that led to a change in study treatment/intervention regardless of grade
- All AEs meeting SAE definition or EAE reporting requirement

NOTE: SAEs or events meeting EAE reporting requirements should also be entered into the DAIDS Adverse Experience Reporting System (DAERS), an internet-based reporting system.

NOTE: At week 24/SVR evaluation visit, information on any AEs participants may have experienced during the prior 24 weeks (particularly while on study medication) will be collected unless this information was already obtained during an unplanned study visit.

All AEs that are reported must have their severity graded. To grade AEs, sites must refer to the Division of AIDS Table for Grading the Severity of Adult and Pediatric Adverse Events (DAIDS AE Grading Table), corrected Version 2.1, July 2017, which can be found on the DAIDS RSC website at <http://rsc.tech-res.com/clinical-research-sites/safety-reporting/daids-grading-tables>.

Serious Adverse Events (SAEs)

A SAE is defined as any untoward medical occurrence that:

- Results in death
- Is life-threatening
- Requires inpatient hospitalization or prolongation of existing hospitalization
- Results in persistent or significant disability/incapacity
- Is a congenital anomaly/birth defect
- Is an important medical event that may not be immediately life-threatening or

result in death or hospitalization but may jeopardize the patient or may require intervention to prevent one of the other outcomes listed in the definition above).

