7.3.2 Reporting Requirements for this Study

- The SAE Reporting Category, as defined in Version 2.0 of the DAIDS EAE Manual, will be used for this study.
- The study agents for which expedited reporting are required are: Sofosbuvir/Velpatasvir (SOF/VEL) FDC
- In addition to the EAE Reporting Category identified above, other AEs that must be reported in an expedited manner are: all cancers, myopericarditis events, hepatic failures, and autoimmune diseases.

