10.2.2 Secondary Outcome Measures

- 10.2.2.1 Participant with at least one unplanned clinic visit prior to SVR evaluation
- 10.2.2.2 Reportable AEs (as per section 7.2 of the protocol) not qualifying as SAEs (see primary safety outcome above), occurring from study entry until 24 weeks following study entry.
- 10.2.2.3 Premature discontinuation of study treatment, as defined by self-report by study participants

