10.6.3 Secondary Outcomes Analysis

Premature discontinuation of study treatment will be defined from participant self-report either via remote contact prior to SVR evaluation, or at an unplanned visit or by retrospective recall at the week 24 or SVR evaluation visit (whichever occurs first). Those participants missing information from all these mechanisms will be assumed to have prematurely discontinued. The proportion of premature study treatment discontinuation will be estimated and a CI calculated to summarize the range of plausible values using methods parallel to other dichotomous outcomes described above.

Non-serious AEs will be summarized by the Medical Dictionary of Regulatory Affairs (MeDDRA) System Organ Class by the reporting types described in section 7.2.

Those who do not achieve SVR with an observed HCV RNA \geq LLOQ will have both baseline and SVR specimens tested for HCV RASs. Participants in this subset with HCV RASs present in their SVR specimen that were not present in their baseline specimen will be enumerated along with the relative frequencies of new RASs. A description of the observed RASs will also be provided.

Among SVR responders, HCV RNA post SVR follow-up (i.e., Step 2) will be used to evaluate for the HCV reinfection outcome. Detectable HCV RNA, with and HCV sequence distinct from the baseline sequence will qualify for the outcome of HCV reinfection. The absolute number (and relative frequency) of participants meeting this outcome will be summarized along with a 95% CI using methods as described for other dichotomous study outcomes.

Among SVR responders, HCV disease regression will be defined by the absolute change between baseline FIB-4 value and the final study FIB-4 value. The distribution of these absolute changes will also be described using key percentiles.

Further details are outlined in the study's Statistical Analysis Plan (SAP).

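### SAP 4.2.2 omits non-serious grade 1–2 events in the four extra EAE categories, which protocol 10.2.2.2 counts through section 7.2

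*SAP*

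**What the plan says.** Protocol 10.2.2.2 defines the secondary safety outcome as "Reportable AEs (as per section 7.2 of the protocol) not qualifying as SAEs", from entry to 24 weeks. Section 7.2 gives three grounds for recording an event: "All grade ≥ 3 AEs"; "All AEs that led to a change in study treatment/intervention regardless of grade"; and "All AEs meeting SAE definition or EAE reporting requirement". Section 7.3.2 adopts the SAE reporting category for expedited reporting and adds "all cancers, myopericarditis events, hepatic failures, and autoimmune diseases". Protocol 10.6.3 plans to summarize non-serious events by MedDRA "System Organ Class by the reporting types described in section 7.2".

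SAP 4.2.2 counts non-serious events "that either had severity grade ≥ 3 or led to a change in study medication". Its measure title carries the same two criteria, its time frame is 28 weeks, and its summary is by SOC and HLT. It does not mention the EAE criterion or the section 7.2 reporting types.

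Separately, protocol 6.3.10 says "Post entry, record the following targeted events regardless of grade". The list that follows includes ascites and hepatic encephalopathy, and a letter of amendment adds variceal bleeding and hepatocellular carcinoma.

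**The concern.** The SAP states that it describes the secondary outcome results to be posted on ClinicalTrials.gov. If its definition is followed exactly, the posted percentage is not the outcome that the protocol defines. The events lost are ones the protocol singled out for expedited reporting whatever their grade, in a study whose purpose is to show that treatment is safe when monitoring is withdrawn. A change to a secondary outcome should be declared and explained, and the SAP does neither.

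A smaller matter sits beside it. Targeted liver events are recorded at any grade, but the SAP does not name them in any outcome or report item.

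**Working it through.** Neither document gives an expected rate for this outcome, so there is no figure to reproduce. The check compares the two definitions and then illustrates the size.

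**Step 1: the two sets.** Let G be grade ≥ 3, T led to a treatment change, S an SAE, and E meets the EAE requirement.

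- Protocol 7.2 reportable events: G ∪ T ∪ S ∪ E. Removing SAEs, as 10.2.2.2 does, leaves (G ∪ T ∪ E) \ S.
- SAP 4.2.2: (G ∪ T) \ S.
- Protocol minus SAP: E \ (G ∪ T ∪ S).

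E consists of the SAE reporting category plus the four categories of section 7.3.2. Taking the SAE reporting category to coincide with SAEs, that part leaves with S. What remains is the four categories when the event is non-serious, grade 1–2 and not treatment-changing. Section 7.3.2 states no grade or seriousness threshold, so this set is not empty by definition.

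| Non-serious event up to week 24 | Protocol 10.2.2.2 | SAP 4.2.2 |
|---|---|---|
| Grade ≥ 3 | counted | counted |
| Grade 1–2, changed treatment | counted | counted |
| Grade 1–2, no change, in one of the four EAE categories (including hepatocellular carcinoma) | counted | **not counted** |
| Grade 1–2, no change, targeted event of 6.3.10 that is not an EAE | not counted | not counted |

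**Step 2: size.** The measure counts participants, so an omitted event matters only when that participant has no other qualifying event. Each such participant shifts the percentage by 1/400 = 0.25 points if the denominator is 400. The SAP denominator is treated participants with at least one post-entry evaluation for adverse events, so it may be somewhat smaller and the shift slightly larger.

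The SAP uses the two-sided 95% Wilson interval, with z = 1.96:

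(p + z²/2n ± z·√[p(1−p)/n + z²/4n²]) / (1 + z²/n)

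As a check of the formula, it returns the limits in protocol Table 10.4-3: 360/400 gives 86.7–92.6%, 380/400 gives 92.4–96.7%, and 392/400 gives 96.1–99.0%.

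The base counts below are assumptions. Each cell shows the percentage and interval after adding back the omitted participants, at n = 400.

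| Assumed SAP count | none added | 1 added | 4 added | 8 added |
|---|---|---|---|---|
| 12 | 3.0% (1.7–5.2) | 3.25% (1.9–5.5) | 4.0% (2.5–6.4) | 5.0% (3.3–7.6) |
| 20 | 5.0% (3.3–7.6) | 5.25% (3.5–7.9) | 6.0% (4.1–8.8) | 7.0% (4.9–9.9) |
| 32 | 8.0% (5.7–11.1) | 8.25% (5.9–11.4) | 9.0% (6.6–12.2) | 10.0% (7.4–13.3) |

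One to four omitted participants move the estimate by 0.25 to 1.0 points, well inside the interval.

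**Step 3: direction.** The missing criterion can only lower the SAP percentage. The longer SAP window, 28 weeks against 24, can only add events. The net difference from the protocol figure is the participants gained from weeks 24 to 28 less those lost through the missing criterion, and the documents do not give its sign.

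**Step 4: targeted events.** A targeted event enters an SAP analysis if it is serious (4.1.2), if it is grade ≥ 3 or treatment-changing (4.2.2), or if it occurs after week 24 (section 6, item 5c, which states no grade limit). What has no named summary is the non-serious, grade 1–2, non-treatment-changing targeted event up to week 24.

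**The case against.** The strongest reply is that the lost set may be close to empty. The SAE definition in section 7.2 includes important medical events, so many cancers, hepatic failures or myopericarditis events would be serious, and others would reach grade 3. This stands as a statement about size. It does not make the definitions agree, and autoimmune disease or a low-grade cancer could still fall through.

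A second reply is that protocol 10.6.3 still calls for a summary by the section 7.2 reporting types, and that table details sit in the Analysis Implementation Plan (AIP), which is not among the documents. That means absence from the final tables cannot be shown. But the SAP describes the AIP as holding table outlines and coding descriptions. The outcome measure itself is defined in SAP 4.2.2.

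Three stronger readings are tempting, and the documents do not support them:

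- *A whole reporting type is lost.* Most of the third section 7.2 criterion is SAEs, which protocol 10.2.2.2 itself excludes and which the primary safety outcome covers.
- *The posted percentage must be lower than the protocol's.* The 28-week window leaves the direction open.
- *Targeted liver events are never analysed.* They are, except for the narrow remainder in step 4. Targeted events are also not a section 7.2 criterion. Leaving them out of SAP 4.2.2 follows the protocol outcome, except where an event is also an EAE, such as hepatocellular carcinoma or an event that counts as hepatic failure.

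**Conclusion.** The mismatch is real and narrow. Followed as written, SAP 4.2.2 yields a percentage that is not the protocol 10.2.2.2 outcome, because it drops without explanation the non-serious, grade 1–2, non-treatment-changing events in the four EAE categories. The expected number is small. The effect is about 0.25 points per affected participant, assuming a denominator of 400 and no other qualifying event in that participant. The net direction against the protocol figure cannot be determined.

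The missing named summary for low-grade targeted events up to week 24 is a minor gap between what is collected and what is analysed. It is not a departure from the protocol outcome, apart from events that are also EAEs.

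**What to change.** In SAP 4.2.2, extend the event definition with a clause such as *or met the EAE reporting requirement of protocol 7.3.2*, and align the measure title. Summarize the events by section 7.2 reporting type as well as by SOC and HLT, as protocol 10.6.3 plans. If the narrower definition is deliberate, the SAP should say so and give the reason.

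Optionally, add to SAP section 6, item 5, a descriptive listing of the 6.3.10 targeted events at any grade up to week 24. No interval or formal subgroup estimate is needed.

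The cost is one clause, a title edit and a split of an existing table, plus one listing if wanted. Section 7.2 already requires the EAE data on the eCRF and 6.3.10 already requires targeted events to be recorded, so nothing new has to be collected.
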